I will conduct the trial in accordance with the clinical investigation plan, Good Clinical Practice guidelines, ISO 14155:2011 (Clinical Investigation of Medical Devices for Human Subjects - Good Clinical Practice), as well as local regulations. I also accept respective revisions to the clinical investigation plan approved by authorized personnel of the Sponsor and by regulatory authorities.

Institution:

[name] [name]

Principal Investigator (Printed name)

Principal Investigator (Signature)

22/2/18

Date

PROTOCOL SUMMARY

TITLE	Clinical Evaluation of the Safety and Performance of Fractional RF for the Treatment of Surgical Scars Following Breast Augmentation, Abdominoplasty or Face Lift
SUMMARY	Split-body/face evaluator-blind study of the safety and performance of fractional RF for the treatment of surgical scars following breast augmentation, abdominoplasty or face lift. The study will enroll up to 50 female subjects requesting treatment of surgical scars following breast augmentation or abdominoplasty and up to 25 male and female subjects requesting treatment of surgical scars following face lift surgery. Subjects will receive a total of three treatments of their surgical scars at one-month intervals on one side of the body or facial incision only. Subjects will be followed up at one, two, three and ten months after their last treatment. Analysis will be performed on all subjects who receive at least one treatment. Outcomes will be compared to the non-treated side.
OBJECTIVES	The objective of this clinical study is to evaluate the safety and performance of fractional RF for the treatment of surgical scars following breast augmentation, abdominoplasty or face lift.

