7.3.2 ENROLLMENT/BASELINE

Enrollment/Baseline Visit (Visit 2, Day 0)

Once a subject has been confirmed that they continue to meet inclusion/exclusion criteria, they will receive a unique identifying number that will be composed of a two-digit site number and a two-digit subject number in sequence. This unique identifier will be used throughout the entire study and will be entered in the subject's case report form (CRF). The investigator will confirm that the subject still meets the inclusion/exclusion criteria. Vital signs and demographics will be collected and a physical exam will be performed. The subject will complete the POSAS.

Photography

Photographs will be taken prior to first treatment and throughout the study according to specified time points detailed in the Schedule of Events Table (section 7.3.7), utilizing standard scientific equipment. Two sets of photographs will be required, one set for the treated side of the body/face and a second set for the untreated side of the body/face.

The photos should be taken in a private room or area of the clinic under controlled conditions, including the distance, angle, background and lighting in order to achieve high-quality sets of photographs. Direct illumination will not be used. The subject should be placed in the same position each time. As each photograph is taken, it should be viewed to ensure that it is in focus and is similar to its baseline counterpart in all technical aspects, including lighting, distance and angle.

For consistency purposes, the same person should ideally take all study photographs, especially per subject. The digital files should follow a consistent standard naming scheme.

Treatment

Subjects will receive treatment as described in section 7.3.1. Only one side of the body/face will be treated. The same side will be treated for the duration of the study. Only half of a scar will be treated

and remaining half will serve as the control. Following treatment, the investigator will examine the treated area and report immediate and short term response. Subjects will complete the 10 cm discomfort/pain VAS immediately after treatment. A new disposal tip will be used for each patient treatment.

Treatment procedure should include positioning of the patient in a manner that enables comfortable access to the treated anatomical site.

Assessment

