7.3.4 FINAL STUDY VISIT

Visit 11, Month 12 (\pm 14 days)

Subjects will return to the clinic seven months after the last assessment. Adverse events, vital signs and any changes to concomitant medications will be recorded. Subjects will complete a 5-point Likert satisfaction questionnaire and the POSAS.

Photographs of the treated area will be taken as described in section 7.3.1. The photographs will be sent to the blinded independent reviewer for assessment (GAIS, MSS and POSAS). The termination form will be completed and subjects will be discharged from the clinic and terminated from the study. The PI will

record all reportable events with start dates occurring any time after informed consent is obtained until 7 (for non-serious AEs) or 30 days (for SAEs) after the last day of study participation.

After the study is completed, subjects will be offered treatment on their untreated side (body/face).

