7.3.7 SCHEDULE OF EVENTS TABLE

Procedures	Screening/Baseline (Visit 1, Day -1)	Enrollment/Treatment (Visit 2, Day 0)	Follow-up (Visit 3, Day 0+2 days)	Treatment & Follow-up (Visit 4, Month 1 (± 7 days))	Follow-up (Visit 5, Month 1+2 days)	Treatment & Follow-up (Visit 6, Month 2 (± 7 days))	Follow-up (Visit 7, Month 2+2 days)	Follow-up (Visit 8, Month 3 (± 7 days))	Follow-up (Visit 9, Month 4 (± 7 days))	Follow-up (Visit 10, Month 5 (± 7 days))	Final Study Visit (Visit 11, Month 12 (± 14 days))
Informed consent	X										
Inclusion/exclusion criteria	X	X									
Demographics	X										
Medical history	X										
Physical exam	X										
Vital signs		X	X	X	X	X	X	X	X	X	X
Urine pregnancy test ^a	X										
Test Spot	X										
Photographs		X						X	X	X	X
Administer Treatment		X		X		X					
Discomfort/Pain VAS	X		X		X						
PI immediate & short-term response	X		X		X						
Blinded reviewer GAIS		X						X	X	X	X
Blinded reviewer MSS	X							X	X	X	X
Blinded reviewer POSAS	X									X	X
Subject POSAS	X									X	X
Subject satisfaction questionnaire										X	X
Concomitant medication	X	X	X	X	X	X	X	X	X	X	X
Adverse event evaluation		X	X	X	X	X	X	X	X	X	X

Procedures	Screening/Baseline (Visit 1, Day -1)	Enrollment/Treatment (Visit 2, Day 0)	Follow-up (Visit 3, Day 0+2 days)	Treatment & Follow-up (Visit 4, Month 1 (± 7 days))	Follow-up (Visit 5, Month 1+2 days)	Treatment & Follow-up (Visit 6, Month 2 (± 7 days))	Follow-up (Visit 7, Month 2+2 days)	Follow-up (Visit 8, Month 3 (± 7 days))	Follow-up (Visit 9, Month 4 (± 7 days))	Follow-up (Visit 10, Month 5 (± 7 days))	Final Study Visit (Visit 11, Month 12 (± 14 days))
^a For women of child-bearing potential.											

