10.2 STATISTICAL HYPOTHESES

The null and alternative hypotheses for the study's primary, key secondary and safety endpoints are;

- Primary Performance Endpoint:
 - **Null Hypothesis ($H_0: \mu_d = \mu_{post} - \mu_{pre} = 0$)** – There is no improvement of surgical scars at 3 months post-treatment review compared to baseline.
Alternative Hypothesis ($H_a: \mu_d = \mu_{post} - \mu_{pre} \neq 0$) – There is improvement of surgical scars at 3 months post-treatment review compared to baseline. The improvement of surgical scars will be defined by General Aesthetic Improvement Scale (GAIS) and Manchester Scar Scale (MSS) scores evaluated by independent blinded reviewer. Expected mean improvement difference is not less than one (1) GAIS and MSS score higher than baseline.
 - **Null Hypothesis ($H_0: \mu_d = \mu_{post} - \mu_{pre} = 0$)** – There is no improvement of surgical scars at 10 months post-treatment review compared to baseline.

Alternative Hypothesis ($H_a: \mu_d = \mu_{post} - \mu_{pre} \neq 0$) – There is improvement of surgical scars at 10 months post-treatment review compared to baseline. The improvement of surgical scars will be defined using General Aesthetic Improvement Scale (GAIS) and Manchester Scar Scale (MSS) scores evaluated by independent blinded reviewer. Expected mean improvement difference is not less than one (1) GAIS and MSS score higher than baseline.

- Secondary Performance Endpoint(s):
 - **Null Hypothesis ($H_0: \mu_d = \mu_{post} - \mu_{pre} = 0$)** – There is no improvement of surgical scars at 1 and 2 months post-treatment review compared to baseline.
Alternative Hypothesis ($H_a: \mu_d = \mu_{post} - \mu_{pre} \neq 0$) – There is improvement of surgical scars at 1 and 2 months post-treatment review compared to baseline. The improvement of surgical scars will be defined using General Aesthetic Improvement Scale (GAIS) and Manchester Scar Scale scores evaluated by independent blinded reviewer.
 - **Null Hypothesis ($H_0: \mu_d = \mu_{post} - \mu_{pre} = 0$)** – There is no improvement of surgical scars at 3 and 10 months post-treatment review compared to baseline.
Alternative Hypothesis ($H_a: \mu_d = \mu_{post} - \mu_{pre} \neq 0$) – There is improvement of surgical scars at 3 and 10 months post-treatment review compared to baseline. The improvement of surgical scars will be defined using Patient and Observer Scar Assessment Scale (POSAS) scores evaluated by independent blinded reviewer.

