10.4.2 ANALYSIS OF THE PRIMARY PERFORMANCE ENDPOINT(S)

The following will be considered for the analysis primary performance endpoint:

Summary table for differences of baseline, 3-month and 10-month post treatment General Aesthetic Improvement Scale (GAIS) and Manchester Scar Scale (MSS) scores will be displayed as mean difference, standard deviation and standard error. The General Aesthetic Improvement Scale (GAIS) scores is a 5-point scale improvement assessment chart while Manchester Scar Scale (MSS) is two scales whose scores are combined - an overall VAS and seven scar parameters.

Bar, pie charts or graphs indicating scores will also be used to analyse performance, where applicable.

All statistical tests will be two-sided. The level of statistical significance for effectiveness analyses is 5% ($\alpha = 0.05$) for all tests of differences. Where appropriate, Paired t-test and/or Wilcoxon Signed-Ranks Test for Matched Pairs will be used to compare the evaluations of General Aesthetic Improvement Scale (GAIS) scores and Manchester Scar Scale (MSS) scores at 3 and 10 months against baseline. Analysis of Covariance (ANCOVA) may also be used where appropriate.

The Paired t-test and/or Wilcoxon Signed-Ranks Test for Matched Pairs will enable us to accept or reject the null hypotheses. Rejection of null hypotheses will establish that:

- The two-sided 95% confidence interval for the difference between the means excludes zero.
- The two means are statistically significantly different at the 5% level ($P < 0.05$) two-sided.

Upon rejection of null hypotheses, further statistical test tools such as Confidence Interval and/or t-test will be used to test expected primary performance endpoint; that is alternative hypothesis that $H_a \geq 1$. This will be used to determine if the study meets the primary performance endpoint.

General Aesthetic Improvement Scale (GAIS) scores and Manchester Scar Scale (MSS) scores of all subjects who received at least one treatment of Venus Viva™ system for the treatment of surgical scars following breast augmentation, abdominoplasty or face lift and for whom at least one valid post-baseline GAIS and MSS assessment were obtained will be analysed for the primary endpoint. Multiple imputation method or modelling of available data may be used for missing data as appropriate.

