10.6.2 EVALUATION OF SUCCESS OF BLINDING

Only the independent reviewers will be blinded. The treating physician and biostatistician or designated party (who conducts interim analysis) will not be blinded.

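### The primary tests are before-after, but the plan does not say that the blinded reviewer is masked to time point, and masking side alone would leave these tests open to reader expectation

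*Combined protocol and SAP*

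**What the plan says.** The trial is described as a split-body/face, evaluator-blind study (Protocol Summary; section 4.1). The blinding rule is in section 10.6.2: "Only the independent reviewers will be blinded". Section 10.6.1 has masking in its heading but covers only subject numbers.

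On the images, section 7.3.2 requires one set of photographs for the treated side and one for the untreated side, and adds "The digital files should follow a consistent standard naming scheme". Under Visit 11, section 7.3.4 says "The photographs will be sent to the blinded independent reviewer for assessment (GAIS, MSS and POSAS"). The schedule in section 7.3.7 marks the row "Blinded reviewer GAIS" at Visits 2, 8, 9, 10 and 11, reviewer MSS at baseline and Visits 8 to 11, and reviewer POSAS at baseline and Visits 10 and 11 only.

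On the contrast, the first primary null hypothesis in section 10.2 is "There is no improvement of surgical scars at 3 months post-treatment review compared to baseline", and the alternative is "There is improvement of surgical scars at 3 months post-treatment review compared to baseline". The 10-month hypotheses have the same form. Section 10.4.2 applies a paired t-test and/or Wilcoxon signed-ranks test to GAIS scores and "Manchester Scar Scale (MSS) scores at 3 and 10 months against baseline". The Protocol Summary says "Outcomes will be compared to the non-treated side", but no hypothesis or test in section 10 uses the untreated side.

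**The concern.** In a split-side trial, a blinded evaluator is usually taken to be one who does not know which side was treated. That protects a comparison of the two sides. It does nothing for a comparison of month 3 or month 10 with baseline on the treated side, because what the reviewer must not know there is which image is the later one. The plan names no safeguard on that point: no coding, no removal of date or visit, no random reading order.

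If the reviewer can tell that an image is a follow-up image and scores it more kindly for that reason, the mean shift adds directly to the estimated improvement. The primary result could then be significant with no device effect.

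**Working it through.** **Inputs from section 10.5.** Two-sided alpha 0.05; power 0.90; expected mean GAIS difference 1.0; SD of the paired difference 1.0 (range 4 ÷ 4); 30% dropout allowance.

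**The plan's own figure.** n = [(z for alpha + z for power) × SD ÷ difference]² = (1.96 + 1.2816)² = 10.51, so 11 per cohort. With dropout, 11 × 1.3 = 14.3, so 15. Both stated figures reproduce. The table prints 0.84 as the z value for 90% power. That value would give (1.96 + 0.84)² = 7.84, so it was not the one used, and it plays no part below.

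**What each form of masking protects.** Let the device effect on the treated side be τ, natural scar change m, and the reader's mean shift in favour of later images b.
- Before-after on the treated side, as in sections 10.2 and 10.4.2, estimates τ + m + b.
- With side masked but time known, b is still there.
- With time masked completely, b = 0 and m remains.
- Treated change minus untreated change estimates τ, provided m and b are the same on both sides. For b, this requires that the reviewer does not know the side.

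**Size.** The documents give no value for b, so 0.25 and 0.5 point are assumptions. Set τ = 0, m = 0 and SD = 1. The two-sided paired t-test then follows a noncentral t distribution with n − 1 degrees of freedom and noncentrality b√n ÷ SD.

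| n | critical t | b = 0 | b = 0.25 (noncentrality) | b = 0.5 (noncentrality) |
|---|---|---|---|---|
| 11 | 2.228 | 5.0% | 11.7% (0.829) | 32.3% (1.658) |
| 15 | 2.145 | 5.0% | 14.7% (0.968) | 43.8% (1.936) |
| 25 | 2.064 | 5.0% | 22.5% (1.250) | 67.0% (2.500) |

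The rows are the calculated cohort size, the size with the dropout allowance, and the face-lift ceiling. More subjects make the error rate worse, because a bias does not shrink with n.

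**What masking leaves behind.** In these formulas m acts exactly as b does. Fully masked, with an assumed natural improvement of 0.25 or 0.5 point, the before-after test still rejects in 11.7% or 32.3% of trials at n=11, and 14.7% or 43.8% at n=15. In a simulation of 20,000 runs per setting (assumed between-side correlation 0.5, same shifts on both sides), the treated-minus-untreated contrast rejected in 4.6% to 5.2% of trials at every setting tested.

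**The case against.** The strongest reply is that the Protocol Summary promises a comparison with the untreated side and section 7.3.2 requires photographs of both sides. With side masked, an expectation shift common to both sides cancels in that contrast. This is correct, and it makes the missing side comparison the larger design problem. It does not rescue the tests as written, because section 10 never uses that contrast.

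A reader might also draw stronger conclusions that the documents do not support:
- **That the reviewer does know the time point.** The documents are silent. A consistent naming scheme need not show date, visit or side; a coded scheme would also comply.
- **That the whole series arrives in one batch at the end.** Section 7.3.4 mentions sending photographs at Visit 11, but section 7.3.7 marks ratings at several visits. The plan does not settle which applies.
- **That masking time would make the before-after test valid.** Section 5.2 admits scars from four weeks after surgery, so scars may change untreated over the follow-up. A young scar may also be recognisable as the earlier image, so masking may be incomplete.
- **That masking is free and applies equally to every scale.** Section 10.4.2 describes GAIS as a 5-point improvement scale. A reader who does not know which image came first cannot score it in the usual way, and a masked pair rating modifies the procedure. Reviewer POSAS is not scheduled at Visits 8 and 9, so reading it on every image would add unplanned assessments.

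**Conclusion.** The concern holds in a limited form. The stated performance tests are before-after, the content of the blind is undefined, and a blind to side alone, which the present text would allow, does not protect them from reader expectation. Whether such bias would occur, and how large it would be, cannot be determined from the documents.

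The illustrative error rates of 11.7% to 43.8% rest on assumed shifts of 0.25 to 0.5 point, the plan's SD of 1.0, normal differences and no natural change. That SD was derived for GAIS; for MSS the shifts should be read as 0.25 and 0.5 of whatever its SD proves to be.

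The change should be made before any image is read. It improves the before-after comparison but does not by itself support attributing the change to the device.

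**What to change.** 1. In section 10.6, state that the reviewer is blinded to both time point and side.
2. Give each image a random code that carries no date, visit or side, and have the key held by someone other than the reviewer.
3. State that images are read in one batch in random order: MSS on all scheduled images, and observer POSAS on the baseline, Visit 10 and Visit 11 images in a separate random-order session, so that the request for POSAS does not hint at the visit. Align sections 7.3.4 and 7.3.7 with this. Section 10.4.7 plans no interim analysis, so no planned analysis needs earlier readings.
4. For GAIS, at least mask side. An option is to show baseline/follow-up pairs in masked random order, ask which looks better and by how much, and decode the sign afterwards. The mapping to the 5-point scale must be fixed in advance.
5. Reconcile section 7.3.2, which requires photographs of both sides, with the text for Visits 8 to 11 in sections 7.3.3 and 7.3.4, which mentions only the treated area and refers to section 7.3.1 for photography. Side cannot be masked at follow-up without images of both sides.
6. Carry the treated-versus-untreated comparison promised in the Protocol Summary into the hypotheses and tests, since masking does not deal with natural scar change.

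For the masking steps, the cost is the coded list, a key holder, a GAIS pair form if that option is taken, and a protocol amendment with ethics approval. No extra reader is needed and the sample size is unchanged.

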7.3.5 EARLY TERMINATION VISIT

Subjects who terminate the study early for whatever reason, will be asked to return to the clinic, if they are willing, to complete the final visit (Visit 11). Adverse events and the reason for early termination will be recorded.

7.3.6 UNSCHEDULED VISIT

If an unscheduled visit occurs, the reason for the unscheduled visit will be documented. If the unscheduled visit is the result of an adverse event, the event will be recorded on the adverse event CRF.

7.3.7 SCHEDULE OF EVENTS TABLE

Procedures	Screening/Baseline (Visit 1, Day -1)	Enrollment/Treatment (Visit 2, Day 0)	Follow-up (Visit 3, Day 0+2 days)	Treatment & Follow-up (Visit 4, Month 1 (± 7 days))	Follow-up (Visit 5, Month 1+2 days)	Treatment & Follow-up (Visit 6, Month 2 (± 7 days))	Follow-up (Visit 7, Month 2+2 days)	Follow-up (Visit 8, Month 3 (± 7 days))	Follow-up (Visit 9, Month 4 (± 7 days))	Follow-up (Visit 10, Month 5 (± 7 days))	Final Study Visit (Visit 11, Month 12 (± 14 days))
Informed consent	X										
Inclusion/exclusion criteria	X	X									
Demographics	X										
Medical history	X										
Physical exam	X										
Vital signs		X	X	X	X	X	X	X	X	X	X
Urine pregnancy test ^a	X										
Test Spot	X										
Photographs		X						X	X	X	X
Administer Treatment		X		X		X					
Discomfort/Pain VAS	X		X		X						
PI immediate & short-term response	X		X		X						
Blinded reviewer GAIS		X						X	X	X	X
Blinded reviewer MSS	X							X	X	X	X
Blinded reviewer POSAS	X									X	X
Subject POSAS	X									X	X
Subject satisfaction questionnaire										X	X
Concomitant medication	X	X	X	X	X	X	X	X	X	X	X
Adverse event evaluation		X	X	X	X	X	X	X	X	X	X

Procedures	Screening/Baseline (Visit 1, Day -1)	Enrollment/Treatment (Visit 2, Day 0)	Follow-up (Visit 3, Day 0+2 days)	Treatment & Follow-up (Visit 4, Month 1 (± 7 days))	Follow-up (Visit 5, Month 1+2 days)	Treatment & Follow-up (Visit 6, Month 2 (± 7 days))	Follow-up (Visit 7, Month 2+2 days)	Follow-up (Visit 8, Month 3 (± 7 days))	Follow-up (Visit 9, Month 4 (± 7 days))	Follow-up (Visit 10, Month 5 (± 7 days))	Final Study Visit (Visit 11, Month 12 (± 14 days))
^a For women of child-bearing potential.											

7.4 JUSTIFICATION FOR SENSITIVE PROCEDURES

This is a non-life-threatening aesthetic treatment with a low potential for serious adverse events.

7.5 CONCOMITANT MEDICATIONS, TREATMENTS, AND PROCEDURES

All concomitant prescription medications taken during study participation will be recorded on the case report forms (CRFs). For this protocol, a prescription medication is defined as a medication that can be prescribed only by a properly authorized/licensed clinician. Other medications to be reported in the CRF are concomitant over-the-counter medications, non-prescription medications and herbal/naturopathic preparations.

7.6 PROHIBITED MEDICATIONS, TREATMENTS, AND PROCEDURES

Use of immunosuppressive medications, anticoagulants, isotretinoin and non-steroidal anti-inflammatory drugs is prohibited.

7.7 PROPHYLACTIC MEDICATIONS, TREATMENTS, AND PROCEDURES

None

7.8 RESCUE MEDICATIONS, TREATMENTS, AND PROCEDURES

In the event that the subject experiences pain, the principal investigator may prescribe any analgesic deemed appropriate to the level of pain. If a subject experiences any first, second or third degree burn or pain beyond narcotics, then the following procedure will be implemented:

- Immediate triage and treatment of the patient shall be determined by the treating physician and based upon severity and type of burn identified.
- The event will be reported to the sponsor study Director within 24 hours of occurrence. If the event meets the criteria of a SAE, then it must be reported on the SAE form.
- An anonymized copy of the patient chart and treatment parameters are to be forwarded to the sponsor study Director within 24 hours.

The sponsor study Director will be responsible for issuing a written report to the company and the EC or IRB Chairman no later than 7 days from the event

Long term follow up and care shall continue at the discretion of the treating physician.

All patients experiencing a complication of the device will be followed a minimum of 2 years following the initial injury. Longer care and observation will be at the discretion of the treating physician.

All minor complications such as appearance or altered sensation, except for pain, can be reported within 30 days of patient complaint. Both chart and treatment parameters are to be provided to the study Director and shared with the company and EC or IRB chairman.

